2.4.3 ANALYSIS OF THE SECONDARY ENDPOINT(S)

Key secondary endpoint, time to recovery:

The primary analysis for time to recovery by Day 28 is an unadjusted log-rank test. Deaths will be considered as never recovering and censored at Day 28. Kaplan-Meier curves and 95% confidence bounds will be provided. If data permit, we may perform a stratified log-rank test where stratification is according to participating site and age (≥ 65 vs < 65 years old), i.e. site and age are randomization stratification factors. We will also perform Cox regression to adjust for baseline patient characteristics (including age, sex, race, Hispanic ethnicity, BMI, hypertension, chronic lung, heart or kidney diseases, immunosuppression). Recovery rate ratio and 95% confidence interval will be provided.

Other secondary endpoints:

- 1) Binary data (e.g., 28-day mortality) will be summarized as a percent with 95% confidence intervals. Comparisons between arms will be presented as differences in proportions with 95% confidence intervals.
- 2) The ordinal scale of patient clinical status will be used to estimate a proportional odds model. The hypothesis test will perform a test to evaluate whether the common odds ratio for treatment is equal to one. If data permit, a test stratified by site will also be performed. The distribution of severity results will be summarized by treatment arm as percentages. Efforts to minimize loss-to-follow-up will be considerable. However, small amounts of missing data may occur. In such cases, subjects without final outcome data will be excluded from the analysis. Sensitivity analyses will evaluate the impact of making different assumptions about missing observations. These analyses will be defined in the Statistical Analysis Plan.
- 3) Differences in time-to-event endpoints (e.g., time to respiratory failure or death and time to at least a one category improvement in the ordinal scale) by treatment will be summarized with log-rank tests, Kaplan-Meier curves and 95% confidence bounds. The same procedure will be used to compare time to at least a two-category improvement. Hazard ratios (for time to respiratory failure or death) or improvement rate ratios (for time to improvement) and 95% confidence intervals will be provided.
- 4) Change in ordinal scale at specific time points will be summarized by proportions (e.g., proportion who have a 1-, 2-, 3-, or 4-point improvement or 1-, 2-, 3-, 4-point worsening).
- 5) Duration of event (e.g., duration of initial hospitalization) will be summarized according to median days with quartiles.
- 6) Categorical data (e.g., ordinal scale by day) may be summarized according to proportions by category and/or odds ratios with confidence intervals.

We recognize that allowing study participants to participate in another SARS-CoV-2 treatment trial after progressing to respiratory failure (**Section 6.5**) may affect the interpretation of the primary intent-to-treat analyses for secondary outcomes (e.g., time to recovery and all-cause mortality), especially if one arm has a higher proportion of respiratory failures, leading to a higher proportion in that arm receiving other SARS-CoV-2 treatments. We will take caution in

the interpretation of results. We will also conduct sensitivity analyses to assess robustness of results, such as incorporating other trial participation as a (time-varying) covariate in the model, imputation, or inverse probability weighting.

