5 STUDY POPULATION

5.1 INCLUSION CRITERIA

Veterans must meet ALL of the following criteria to be eligible to participate:

1. Admitted to a participating VA clinical site with symptoms suggestive of SARS-CoV-2 infection.
2. Participant (or legally authorized representative) provides informed consent prior to initiation of any study procedures.
3. Participant (or legally authorized representative) understands and agrees to comply with planned study procedures.
4. Veteran \geq 18 years of age at time of screening.
5. Has laboratory-confirmed SARS-CoV-2 infection as determined by polymerase chain reaction (PCR) or antigen test, as documented by either of the following:
 - (1) RT-PCR or antigen positive (nasopharyngeal, oropharyngeal, saliva, lower respiratory) in sample collected \leq 72 hours prior to screening;
 - (2) RT-PCR or antigen positive in sample collected $>$ 72 hours but \leq 168 hours (i.e. 7 days) prior to screening, documented inability to obtain a repeat sample (e.g. due to lack of testing supplies, limited testing capacity, results taking $>$ 24 hours, etc.), AND progressive disease suggestive of ongoing SARS-CoV-2 infection.
6. Requiring oxygen by nasal cannula or by face-mask as a new treatment (or if previously on home oxygen, at a liter flow at least 2 Lpm greater than home prescription), but not on humidified heated high-flow nasal cannula (HHHFNC) at \geq 15 Lpm.
7. Can be randomized within 72 hours of initial hospital admission.
8. Agrees not to participate in another therapeutic clinical trial for the treatment of COVID-19 or SARS-CoV-2 through Day 29 without approval from the investigator(s). Taking part in other research studies, including those unrelated to SARS-CoV-2, without first discussing it with the investigators of this study may invalidate the results of this study, as well as that of the other study.

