6.5 CONCOMITANT THERAPY

Therapy prior to enrollment with any other experimental treatment or off-label use of marketed medications that are intended as specific treatment for SARS-CoV-2 infection (i.e., post-exposure prophylaxis) are permitted.

Participants who are taking remdesivir for COVID-19 or another antiviral for a concurrent infection (e.g. oseltamivir for an influenza virus, lopinavir/ritonavir for HIV, etc.), or

immunosuppressive drugs for other medical conditions (corticosteroids for an unrelated condition, tocilizumab for rheumatoid arthritis, hydroxychloroquine for lupus, etc.) may continue with the treatment.

Participants entering the trial may be prescribed therapy for SARS-CoV-2 that has received preliminary FDA approval whether available by prescription or under an expanded access program (EAP), e.g. remdesivir or dexamethasone. These medications may be initiated or continued. However, participants may not have previously received or be given SARS-CoV-2 convalescent plasma under the Mayo or any other EAP.

A participant cannot participate in another clinical trial for the treatment of SARS-CoV-2 until after Day 29. However, if the participant has progressed to respiratory failure in the hospital (see definition in *Section 3*), another experimental treatment protocol may be initiated, but only if there is a sponsor-approved agreement between the leadership of both trials. The agreement will consider potential impact of dual enrollment on study outcomes and participant safety and establish procedures to coordinate adverse event monitoring and reporting of dual-enrolled participants.

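### One of three example sensitivity analyses for co-enrolment adjusts for a consequence of respiratory failure, so it can remove part of the plasma effect that it is meant to test

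*Combined protocol and SAP*

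**What the plan says.** Section 6.5 sets the general rule: "A participant cannot participate in another clinical trial for the treatment of SARS-CoV-2 until after Day 29". The exception applies "if the participant has progressed to respiratory failure in the hospital", and then "another experimental treatment protocol may be initiated, but only if there is a sponsor-approved agreement between the leadership of both trials". Table 2 in Section 3 makes respiratory failure, with death, the primary endpoint.

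Section 9.4.3 (printed as 2.4.3) recognises that this exception can disturb the intention-to-treat analyses of secondary outcomes; mortality and recovery time are its examples. The plan describes the path itself: "especially if one arm has a higher proportion of respiratory failures, leading to a higher proportion in that arm receiving other SARS-CoV-2 treatments". It promises cautious interpretation and sensitivity analyses, with three examples. The first is "incorporating other trial participation as a (time-varying) covariate in the model"; the others are weighting by inverse probability and imputation. It does not choose among them, state an estimand or list variables for the weights. Section 9.4.1 leaves the detail to a statistical analysis plan to be written before unblinding.

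**The concern.** Other-trial participation arises after randomisation and, under Section 6.5, only in patients who have already failed. If plasma prevents failure, fewer plasma patients can ever carry the covariate. Adjusting for it compares arms partly among patients of equal failure status, which takes out benefit that plasma achieved by preventing failure. Coding the covariate as time-varying avoids immortal-time bias but does not cure this.

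A robustness check should leave the estimate alone when co-enrolment does nothing. This one need not. A sound recovery or mortality result could look fragile, and a harmless second treatment could look dangerous, because everyone who receives it has already failed.

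**Working it through.** **The plan's own figure.** No figure is given for the sensitivity analysis. The nearest is Table 8: 83% power for a recovery rate ratio of 1.3, with 70% recovery among 702. Expected recoveries are 0.70 × 702 = 491. Power = Φ(√(491/4) × ln 1.3 − 1.96) = Φ(11.08 × 0.262 − 1.96) = Φ(0.95) = 83%. It reproduces.

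**Mechanism.** The model is λ(t) = λ₀(t) exp(βA + γZ(t)), where A is the arm and Z(t) becomes 1 at co-enrolment. Everyone with Z = 1 has failed, so that stratum contains no difference between arms in failure status. In the stratum with Z = 0, if a share q of failures co-enrols and f is the failure proportion, the share who have failed is f(1 − q)/(1 − fq). As an upper bound for f, take the plan's 30% and 20% (Section 9.2); these also include deaths without failure.

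| q (assumed) | Control, Z = 0 | Plasma, Z = 0 | Difference |
|---|---|---|---|
| 0 | 30.0% | 20.0% | 10.0 points |
| 10% | 0.27/0.97 = 27.8% | 0.18/0.98 = 18.4% | 9.5 |
| 40% | 0.18/0.88 = 20.5% | 0.12/0.92 = 13.0% | 7.4 |
| 100% | 0 | 0 | 0 |

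The contrast that carries the benefit shrinks as uptake rises and is gone at 100%.

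**Size.** The documents give neither uptake nor the effect of the other treatment, so both are assumptions. Cox models were fitted to simulated patients with and without Z(t), with an inert other treatment and plasma acting only by preventing failure. Simulation B has 300,000 patients per scenario, about 31.5% vs 21.6% primary events and 73% recovery.

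| Uptake among failures | A: mortality HR | A: recovery ratio | B: mortality HR | B: recovery ratio |
|---|---|---|---|---|
| Unadjusted | 0.70–0.71 | 1.10 | 0.68 | 1.11 |
| 10% | 0.73 | 1.10 | 0.70 | 1.10 |
| 20% | 0.75 | 1.09 | – | – |
| 30% | – | – | 0.74 | 1.09 |
| 40% | 0.80 | 1.08 | – | – |
| 50% | – | – | 0.82 | 1.07 |
| 100% | 1.01 | 1.00 | 0.97 | 1.02 |

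Share of the log effect removed in A, taking 0.70 as the start:
- Mortality at 10%: 1 − ln 0.73/ln 0.70 = 1 − 0.315/0.357 = 12%.
- Mortality at 40%: 1 − 0.223/0.357 = 37%.
- Recovery at 40%: 1 − ln 1.08/ln 1.10 = 1 − 0.077/0.095 = 19%.

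In A the inert treatment itself shows a spurious mortality hazard ratio of 6.6 or more.

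**Variations, run in the setting of B.**
- Adding a direct plasma effect of 1.25 on recovery: 1.36 becomes 1.35 at 10% uptake, and 1.34 becomes 1.25 at 100%. At full uptake only the direct effect remains.
- Other treatment with a 1.5-fold benefit: both ratios still move toward the null.
- Threefold benefit at 50% uptake: recovery ratio essentially unchanged, 1.07 and 1.07.
- Sixfold benefit at 50% uptake: recovery ratio moves away from the null, 1.04 to 1.07.

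The mortality hazard ratio is a stand-in. Section 9.4.3 summarises 28-day mortality as a binary outcome with a difference in proportions, and a time-varying covariate needs a hazard model.

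**The case against.** The strongest reply is that nothing is committed. The covariate model is one of three examples, the weighting recommended below is already another of them, and the plan itself names the dependence on respiratory failure and promises caution. That stands, and it limits the severity. It does not make the covariate model a valid example: the plan describes the causal path and then lists a method that cannot handle it.

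Four stronger readings are tempting, and the documents do not support them.

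- *That the model conditions on the primary outcome itself.* The covariate marks only the failures who co-enrol, and Section 6.5 also requires an agreement between the trials. It is a consequence of failure, not failure itself, and the bias scales with an uptake that is nowhere stated.
- *That the estimate must move toward the null.* This is usual when the other treatment is inert or modestly effective, but the sixfold scenario goes the other way.
- *That co-enrolment can occur only after failure.* This rests on Section 6.5. Inclusion criterion 8 (Section 5.1) lets a participant join another therapeutic trial with the investigators' approval and does not mention respiratory failure.
- *That the trial's main results are at risk.* Under Section 6.5 the primary endpoint, and time to death or respiratory failure, are reached before co-enrolment. The intention-to-treat analyses do not use the covariate.

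It is also fair to say that the shift is small against sampling error at low uptake. Assume 75 deaths among 702: SE(log HR) = 2/√75 = 0.23. Moving from 0.70 to 0.73 is then 0.042/0.23 = 0.2 SE, and to 0.80 it is 0.134/0.23 = 0.6 SE. For recovery, SE = 2/√491 = 0.09, and moving from 1.10 to 1.08 is 0.018/0.09 = 0.2 SE. This tempers the consequence. However, both estimates come from the same patients, so the gap between them is systematic, and that gap is what a reader would take as evidence on robustness.

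**Conclusion.** The point holds as a minor one. Ordinary time-varying adjustment for other-trial participation is not a sound check of the recovery or mortality results, because it removes part of any effect that runs through preventing respiratory failure. With an inert other treatment and plasma acting only through failure, the distortion is slight at 10% uptake (mortality hazard ratio about 0.70 to 0.73, recovery ratio 1.10 unchanged to two decimals). It is moderate at 40% (0.80 and 1.08) and complete at 100% (about 1.0 for both). These sizes depend on assumed uptake, mechanism and effect of the other treatment; a direct plasma effect on recovery would survive the adjustment. Only sensitivity analyses of secondary outcomes are touched.

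**What to change.** 1. In Section 9.4.3, delete the covariate option, or label it descriptive and not a test of robustness.
2. Keep intention-to-treat as the main analysis.
3. Make inverse probability weighting the prespecified sensitivity analysis. Censor at co-enrolment. Build the weights from time-updated respiratory failure status and the daily clinical-support data in Section 8.3.1. State the estimand: the effect on recovery or mortality had nobody entered another trial.
4. Reconcile inclusion criterion 8 with Section 6.5 on when co-enrolment is possible. If entry without respiratory failure can occur, the weight model must cover it.

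Cost: a short text change plus a weight model to specify and run. No change to sample size is needed. The clinical variables are already collected; the date of co-enrolment is needed too, as it is for the covariate model. The downside is precision. The weights may be unstable or poorly estimated if few patients co-enrol or if some sites have no agreement with another trial. They break down if nearly all failures co-enrol, because nobody is left to stand in for those censored. The plan should say how large weights will be handled and that the analysis is supportive only.

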2.4.4 SAFETY ANALYSES

AEs and SAEs will be coded using the Medical Dictionary for Regulatory Activities (MedDRA), counted both at the patient level and event level. Severity, frequency, and relationship of AEs and SAEs to study intervention will be presented by System Organ Class (SOC) and preferred term groupings. We will compare the proportions of participants experiencing an SAE, treatment related non-serious AEs, SARS-CoV-2 related adverse events of grade 3 severity, or non-serious adverse events of grade 3, by Chi-square test or Fisher's exact test, as appropriate.

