8.5 ADVERSE EVENTS AND SERIOUS ADVERSE EVENTS

Timely and complete reporting of safety information assists study management in identifying any untoward medical occurrence, thereby allowing: a) protection of safety of study participants; b) a greater understanding of the overall safety profile of the study treatments and therapeutic modalities; c) improvements in study design or procedures; and d) consistency with Good Clinical Practice.

All serious adverse events and the following non-serious adverse events will be collected and reported to the sponsor on study CRFs:

- Treatment-related adverse events of any severity: transfusion reaction (fever, rash), transfusion related acute lung injury (TRALI), transfusion associated circulatory overload (TACO), transfusion related infections.
- Adverse events that have a grade 3 severity, regardless of attribution;

- SARS-CoV-2 related adverse events and have a grade 3 severity, regardless of attribution: cardiac arrhythmias, cardiac arrest, need for ECMO or ventricular assistance, thromboembolic or thrombotic complications, need for intensive medical care, need for increased oxygen support or mechanical ventilation, sustained low blood pressure requiring IV pressure support.

These events will be collected and reported on study CRFs from the time of randomization and until becoming lost to follow-up, discontinuing study participation early, or completing the final study visit, whichever occurs first. Details are described below.

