8.5.2 DEFINITION OF SERIOUS ADVERSE EVENTS (SAE)

An AE is considered an SAE if, in the view of either the investigator or sponsor, it results in any of the following outcomes:

- Death;
- A life-threatening experience;
- Inpatient hospitalization or prolongation of existing hospitalization;
- A persistent, significant, or permanent incapacity or substantial disruption in the participant's body function/structure, physical activities and/or quality of life;
- Congenital anomaly/birth defect; or
- Important medical events that may not be immediately life-threatening, result in death, or require hospitalization may be considered serious when, based upon appropriate medical judgment, they may jeopardize the participant and may require medical or surgical intervention to prevent one of the outcomes listed in this definition. Such events include intensive treatment in an emergency room or at home for allergic bronchospasm; blood dyscrasias or convulsions that do not result in hospitalization; or development of drug dependency or drug abuse. (See 21 CFR 312.32(a) and VHA Handbooks 1058.01 and 1200.05)

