8.5.3.1 EXPECTEDNESS

An AE that is new or greater than previously known, in terms of nature, severity, or frequency of occurrence, or any other unanticipated serious problem associated with the investigation that relates to the rights, safety, or welfare of subjects, as documented in the protocol or other materials approved by the IRB of record or the characteristics of the study population. Such

materials may include but are not limited to: the informed consent form, safety plan, clinical investigator's brochure (or CSPCPRCC's Drug Information Report), and product labeling (see VHA Handbook 1058.01). The Sponsor will concur or disagree with the site investigator's assessment as to whether an adverse event is anticipated or unanticipated (sometimes referred to as expected/unexpected, respectively).

The following AEs are considered uncommon, but **anticipated** in this study population:

- Related to the study intervention: transfusion reaction (fever, rash), transfusion related acute lung injury (TRALI), transfusion associated circulatory overload (TACO), transfusion related infections.
- Related to COVID-19 disease progression: cardiac arrhythmias, cardiac arrest, need for ECMO or ventricular assistance, thromboembolic or thrombotic complications, need for intensive medical care, need for increased oxygen support or mechanical ventilation, sustained low blood pressure requiring IV pressure support.

As these AEs will be considered anticipated, they will not generally require expedited reporting to the CIRB. The frequency of these events will be monitored regularly during aggregate data review. In the event the frequency of any of these events is identified to be greater than anticipated during aggregate analysis, the event will then be reported as a serious unanticipated problem.

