2.3 POPULATIONS FOR ANALYSES

The primary analysis will be based on an intention-to-treat population, including all participants randomized. The safety analysis will be based on a modified intent-to-treat population consisting of all participants who received at least one dose of any study intervention.

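### Treatment-related events are compared between arms only when non-serious, so serious transfusion injury has no between-arm estimate of its own and is compared only within all SAEs

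*Combined protocol and SAP*

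**What the plan says.** The between-arm safety comparison reads "We will compare the proportions of participants experiencing an SAE, treatment related non-serious AEs, SARS-CoV-2 related adverse events of grade 3 severity", and the sentence goes on to non-serious grade 3 events. The test is chi-square or Fisher's exact. The safety population is the "modified intent-to-treat population consisting of all participants who received at least one dose of any study intervention" (Populations for Analyses, printed as 2.3).

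Section 8.5 states "All serious adverse events and the following non-serious adverse events will be collected and reported to the sponsor on study CRFs", with no exemption for primary-endpoint events. Under 8.5.2 an event is serious if, among other outcomes, it is "A life-threatening experience" or results in "Inpatient hospitalization or prolongation of existing hospitalization".

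Section 8.5.3.1 already separates two lists of anticipated events. One is "Related to the study intervention: transfusion reaction (fever, rash), transfusion related acute lung injury (TRALI), transfusion associated circulatory overload (TACO), transfusion related infections". The other begins "Related to COVID-19 disease progression: cardiac arrhythmias, cardiac arrest, need for ECMO or ventricular assistance" and also covers intensive care, increased oxygen support and mechanical ventilation.

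Safety Analyses also plans a display: "Severity, frequency, and relationship of AEs and SAEs to study intervention will be presented by System Organ Class (SOC) and preferred term groupings". Section 9.4.6.1 gives the DMC a similar presentation by treatment group at the interim analyses and at least every 6 months.

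**The concern.** Once a TRALI, TACO or transfusion reaction becomes serious, it leaves the treatment-related comparison. The plan therefore pre-specifies a comparison for the milder product-related events and none for the graver ones.

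The class that the graver events enter is a poor place to see them. Every participant is hospitalized with COVID-19 and on oxygen. Death is serious by definition, and a need for ventilation or ECMO will often be life-threatening or prolong the stay. If plasma delivers the planned benefit, fewer progression events on plasma would offset added transfusion injuries in the same count. The transfusion list and the progression list exist, but the comparison does not use them to divide the SAEs.

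At stake is the product-specific safety statement at the end of the trial: a class-level difference with its uncertainty, chosen before unblinding.

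**Working it through.** **Inputs from the documents.**
- 1:1 allocation; 666 evaluable participants (333 per arm); 702 randomized (351 per arm if all are dosed).
- Planned death or respiratory failure of 30% on saline and 20% on plasma (Sample Size Determination). No SAE rate is stated, so these serve as a proxy for progression SAEs.
- Serious events within 4 hours of transfusion below 1% (2.3.1). No rate through Day 29 is given.

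**Assumptions.** Two-sided 0.05 for the safety tests, for which no level is stated; serious transfusion-injury rate t, shown as a range; injury independent of progression.

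**Plan's own figure.** n per arm = (1.960 + 1.036)² × (0.30×0.70 + 0.20×0.80) / 0.10² = 332.2, rounded up to 333, or 666 in total. This reproduces the plan.

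**Formulas.** Any-SAE rate in an arm = p₀ + (1 − p₀)t, where p₀ is the rate of other SAEs. With d = plasma − saline, the power of the pooled test to show harm is Φ{[d − 1.96√(2p̄(1−p̄)/n)] / √[(p_S(1−p_S) + p_P(1−p_P))/n]}. For significantly fewer SAEs on plasma, replace d by −d. The separate test is Fisher's exact, with power by enumeration over two binomials.

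**Scenario A: t = 4% vs 0.5%, 333 per arm.**
- Without benefit, p₀ = 30%: saline 0.30 + 0.70×0.005 = 30.35%; plasma 0.30 + 0.70×0.04 = 32.8%; d = 2.45 points. Both standard errors are 0.0360, so power = Φ[(0.0245 − 0.0706)/0.0360] = Φ(−1.28) = 10%. At p₀ = 35% and 40% it is 9% and 8%.
- Separate Fisher test: 86%. At 3% vs 0.5% the figures are 62% separate and 6–7% pooled.
- With the planned 10-point benefit: plasma 0.20 + 0.80×0.04 = 23.2% vs 30.35%. The pooled test declares fewer SAEs on plasma with probability 55% (53% and 52% from saline bases of 35% and 40%), despite a 3.5-point excess of serious transfusion injury.

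**Scenario B: no such events on saline, 351 per arm.**

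| t on plasma | Any SAE on plasma, with benefit (saline 30%) | P(significantly fewer SAEs on plasma), with benefit | Pooled power to show harm, no benefit (30% vs 30%) | Separate Fisher power |
|---|---|---|---|---|
| 0.5% | 20.4% | 84% | 3% | 0.9% |
| 1% | 20.8% | 80% | 4% | 14% |
| 2% | 21.6% | 72% | 6% | 70% |
| 3% | 22.4% | 63% | 9% | 95% |
| 5% | 24.0% | 43% | 17% | >99% |

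With 333 per arm the separate test has 12% power at 1% and 66% at 2%. It needs at least 6 vs 0 events for p < 0.05 (p = 0.031; 5 vs 0 gives 0.062). A background of 0.3% on saline lowers its power at 351 per arm to 6%, 43% and 78% at t = 1%, 2% and 3%.

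Under the planned benefit the any-SAE difference is zero when 0.20 + 0.80t = 0.30, that is t = 12.5%, or about 44 of 351 plasma participants.

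**The case against.** **Serious related events are already displayed.** The tables cover the relationship of SAEs to the intervention by preferred term, and the DMC receives safety summaries by arm. Section 8.5.3.1 monitors the listed events in aggregate, and the Safety Management Team assesses SAEs in real time. This stands. A reader might infer that the plan conceals serious transfusion injury; the documents do not support that. What is missing is narrower: a class total with a between-arm estimate. Transfusion reaction, TRALI, TACO and infection may fall on different preferred-term rows, and no rule says how to add them up.

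**The rates that make a separate test look strong have no source.** This also stands. Section 2.3.1 gives less than 1% for serious events, though only within 4 hours and in another cohort. A reader might infer that a separate test would reliably detect harm. At 1% it would not.

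**Dominance by progression is inferred.** No SAE rate is stated, and 8.5 lists events such as cardiac arrest and mechanical ventilation among the non-serious grade 3 events to collect. How much progression would be recorded as serious is uncertain, although 8.5.2 would make much of it so.

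**Fewer total SAEs despite some transfusion harm is a correct net result.** Agreed. The any-SAE comparison is valid for overall serious harm; it is only uninformative about cause.

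**Detail is deferred.** Section 9.4.1 promises a later analysis plan, and the DMC's data elements are to be set at its organizational meeting. Neither is available here, so it cannot be said that they omit this class. The current text nevertheless names specific comparisons and leaves it out.

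**Conclusion.** The gap is real and limited. The comparison of treatment-related events stops at the non-serious ones; serious ones are tabulated but have no named between-arm estimate. The pooled SAE comparison does not fill the gap. Without benefit it has 3–17% power to show harm for injury rates of 0.5–5%. With the planned benefit it points towards plasma until the injury rate exceeds 12.5%.

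The size of the gain from a separate comparison depends on an unknown rate. Near 1% it is mainly an interpretable risk difference and interval; from about 2% the test itself becomes useful if such events are absent on saline. These figures rest on 333–351 dosed per arm, 30% and 20% as a proxy for progression SAEs (30–40% as the base in Scenario A), independence of injury and progression, and two-sided 0.05. The primary efficacy result is not affected. The change is worth making because safety is a stated aim and the remedy is nearly free.

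**What to change.** In Safety Analyses (9.4.4, printed as 2.4.4):

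1. Replace the class of treatment-related non-serious events with treatment-related events, defined by the 8.5.3.1 transfusion list, regardless of seriousness.
2. Show treatment-related SAEs as a separate row.
3. Give each row a risk difference with an exact 95% CI, and use the same rows in the DMC tables.
4. Optionally, report SAEs without COVID-19 progression and primary-endpoint events beside total SAEs. Keep in that count every event that is on the transfusion list or judged definitely or possibly related, even if the patient was ventilated or died. Otherwise the exclusion would remove the worst transfusion injuries.

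The cost is a wording change and two extra table rows. Seriousness, relatedness and event type are already collected, so no new data, visits or participants are needed. One limit remains: the related class depends on investigator attribution, which is hard to make in this disease but is made by blinded site investigators.
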